6.2. Important Protocol Deviations

The number and percentage of subjects with important protocol deviations will be categorized and tabulated as appropriate for the ITT population. COVID-19-related important protocol deviations will be summarized in a separate table. All protocol deviations will be finalized prior to unblinding.

A subset of pre-specified major protocol deviations will exclude some patients in the PPS analyses if these deviations significantly impact efficacy analyses. These major PDs will be reviewed and finalized by following FibroGen medical review process prior to database lock and unblinding. Considerations will be given according to the following table.

Confidential Page 20 of 56

Number	Major Protocol Deviation
1	Violation of any inclusion or exclusion criteria that may affect the assessment of
	efficacy or safety of the study drug*
2	Withdrawal Deviation: Subject met withdrawal criteria during the study but was
	not withdrawn*
3	Dosing Deviation: Subject received the wrong treatment or incorrect dose,
	including incorrect timing of a dose, which may affect the assessment of efficacy
	or safety of the study drug*
4	Administration of prohibited concomitant medication that may impact evaluation
	of efficacy of the study drug*
5	Significant noncompliance with study procedures that may impact evaluation of
	efficacy of the study drug will be evaluated case by case*

Table 1: Criteria for Major Protocol Deviations

6.3. Demographics and Baseline Characteristics

6.3.1. Demographics and Baseline Characteristics

Demographics and important baseline characteristics will be summarized for the ITT by treatment arm and all pooled. These may include but are not limited to age, age group (≤64, 65-74, ≥75), sex, ethnicity, race group, weight, body mass index (BMI), smoking history, prior treatment with an approved IPF therapy (Yes/No), GAP stage (I, II, III), and years since the first diagnosis of IPF. Age is defined as the age on the day of signing the informed consent form (ICF). Years since the first diagnosis will be derived using the formula: date of ICF- date of IPF diagnosis+1. Partial missing date of IPF diagnosis will be imputed as Jan. 01 (if month is missing), or 01 (if day is missing).

Baseline values for efficacy assessments will be presented in baseline tables as appropriate.

Comparability of baseline characteristics between treatment groups will be assessed using analysis of variance (ANOVA) model for continuous variables and Chi-squared test for categorical variables. The nominal p-values will be presented for reference only.

6.3.2. Medical History

Medical History coded by Medical Dictionary for Regulatory Activities (MedDRA, Version 25.0 or higher) will be summarized for the ITT Population.

6.4. Prior and Concomitant Medications

The latest World Health Organization Drug Dictionary (WHODD Global B3 Mar2022, or higher version) will be used to classify prior and concomitant medications by therapeutic class and preferred term.

Prior medication is defined as any medication taken and stopped prior to the first dose of the study drug. Concomitant medication is defined as any medication taken after the first dose of the Confidential

Page 21 of 56

^{*} Major PDs will be reviewed and finalized by following FibroGen medical review process; these five categories may not cover all IPDs.

study drug and before the last dose days +60 days. For subjects who are treated in the OLE, medications that started after 1st dose in the OLE period may be considered as concomitant medication for the OLE period, but not for the double-blind period. Partially or incompletely missing prior/concomitant medication start or stop dates will be imputed (Appendix 1). Table 2 provides the classification guideline when medication starting or ending dates are missing.

Table 2:	Classification	of Dwinn and	Canaamitant	Madiantiana
rabie z:	Ciassification	of Prior and v	Concomitant	vieuications

End Date Start Date	Before start of study drug administration	On or after start of study drug administration	Missing
Before start of study drug administration	Prior	Concomitant	Concomitant
On or after start of study drug administration and before the last dose date +60 days	-	Concomitant	Concomitant
Missing	Prior	Concomitant	Concomitant

Both prior and concomitant medication usage will be summarized by the number (%) of subjects receiving the drug within each therapeutic class and ATC code level 3 and preferred term for the SAF. Multiple usages of the same drug by a patient will be counted only once.

Separate summaries may be provided for prior and concomitant medications of special interest such as the approved IPF medications (pirfenidone and/or nintedanib).

To evaluate the use of co-administered medications that are narrow therapeutic CYP substrates, the concomitant medication for narrow therapeutic index cytochrome P450 substrates will be listed and summarized. The list of related medications will be finalized prior to database lock.

6.5. Prior and Concomitant Procedures and Non-drug Therapies

Procedures and non-drug therapies were coded with MedDRA Version 25.0 or higher version. Prior/Concomitant procedures and non-drug therapies will be defined and summarized similarly to prior and concomitant medications (Details in Section 6.4). Partially or incompletely missing procedures and non-drug therapies start or stop dates will be imputed similarly to prior/concomitant medications (Appendix 1).

6.6. Study Drug Exposure and Treatment Compliance

6.6.1. Study Drug Exposure

Exposure to the study drug will be summarized in terms of treatment duration for the SAF.

Duration of study treatment in weeks is calculated as: (last dose date – first dose date + 1)/7.

Duration of study treatment will be summarized as a continuous variable and be tabulated by the categories as follows:

- <6 weeks
- 6 to <12 weeks
- 12 to <18 weeks

Confidential Page 22 of 56

- 18 to <24 weeks
- 24 to <36 weeks
- \geq 36 weeks

Number (%) of subjects by the total number of infusions $(1-3, 4-6, 7-9, 10-12, \ge 13)$ received, overall average infusion doses (in mg/kg), whether infusion was missed/interrupted and reason for missed/interruption, and patient-exposure years (PEY) will be summarized for the SAF.

6.6.2. Treatment Compliance

The compliance will be presented as % of the actual dose administered out of the total planned dose of infusions by end of study (EOS) or by discontinuation in subjects who discontinued.

$$Compliance~(\%) = \frac{actual~total~dose~received}{total~planned~dose~while~actively~in~treatment} \times 100$$

Descriptive statistics for study drug compliance will be presented by treatment group for the SAF. Treatment compliance will be summarized as a continuous variable and as a categorical variable (<70%, 70% –<80%, 80% –<90%, 90%-110%, and >110%).

6.7. Efficacy Analysis

The primary and secondary endpoints will be tested using a fixed sequence analysis approach to preserve the study-wide error rate of 5%. Under the sequential analysis, the primary and secondary efficacy endpoints will be tested in a defined sequence according to the order listed in Table 3 each at the usual alpha= 0.05 level of statistical significance. The testing will cease when a failure occurs in the pre-determined sequential hypothesis testing and all p-values for the subsequent testing will be considered nominal. All p-values for exploratory endpoints will be considered nominal.

All analyses for efficacy endpoints will be performed for the ITT population during the On-Study period (Section 5.3.1.1), unless noted otherwise. The placebo group will be used as the reference group for all treatment comparisons.

Confidential Page 23 of 56

Testing Endpoints order Change in FVC (L) from baseline at Week 48 (**Primary Endpoint**) 2 Time to disease progression, defined as absolute FVCpp decline of $\geq 10\%$ or death, whichever occurs first 3 Time to the occurrence of any component of the clinical composite endpoint: acute IPF exacerbation, respiratory hospitalization, or death (whichever occurs first) Change in QLF volume from baseline at Week 48 4 Time to first acute IPF exacerbation during study Time to all-cause mortality during study 6 Time to first respiratory hospitalizations during study

Table 3: Fixed Sequence Testing Order of Primary and Secondary Endpoints

6.7.1. Primary Endpoint Analysis and Estimand

The primary endpoint is change from baseline in FVC (L) at Week 48.

The hypotheses to be tested for the primary efficacy analysis is:

 H_0 : Change from baseline in FVC (L) at week 48 for the pamrevlumab arm = Change from baseline in FVC (L) at week 48 for the placebo arm

Versus:

 H_1 : Change from baseline in FVC (L) at week 48 for the pamrevlumab arm \neq Change from baseline in FVC (L) at week 48 for the placebo arm

6.7.1.1. Primary Analysis with MMRM

6.7.1.1.1. Estimand Strategy

The primary estimand is intended to provide a population level estimate of the treatment effect of the pamrevlumab on a continuous endpoint, regardless of participant compliance with the IP (investigational product) dosing.

6.7.1.1.2. Population of Interest

The ITT population includes all randomized subjects during the on-study period as defined in Section 5.3.1.1. Male and female patients aged 40 or above with IPF diagnosis under American Thoracic Society/European Respiratory Society (ATS/ERS) criteria (Raghu 2018), and not currently receiving treatment with the 2 approved antifibrotic standard of care medications.

6.7.1.1.3. Intercurrent Event Handling Strategy

Treatment discontinuation due to non-death reasons: Treatment policy strategy will be used. Missing data are assumed to be missing at random.

Confidential Page 24 of 56

Death: Post-death FVC values will be set as the worst (lowest) post-baseline FVC values across all randomized subjects in the double-blind period. Missing study day will be imputed as the target day of each analysis visit.

6.7.1.1.4. Analysis Variable

Change from baseline in all FVC assessments in the double-blind period, including scheduled, unscheduled, and available assessments after treatment discontinuation, up to week 48 during the On-Study period (Section 5.3.1.1), will be included in the analysis.

In the situation where a subject has more than one record of FVC within an analysis visit, the best value will be used for MMRM.

6.7.1.1.5. Population Summary for Treatment Comparison

Treatment difference of Least-square mean (LSMean) and SE at week 48 and the corresponding 95% CI will be presented.

All post-baseline visits for the specified parameters below during the double-blind period will be included in the analysis. Change from baseline for the specified endpoints (excluding baseline visits) will be analyzed using a Mixed Model for Repeated Measures (MMRM) approach with fixed effects for treatment, visit (as a factor), treatment-by-visit interaction, randomization stratification factor, and covariates (baseline values, sex, age, race group, and height). Example SAS code in Appendix 7.1.

The following graphical displays will be provided:

- The mean $(\pm SE)$ FVC over time by treatment group
- The mean (± SE) FVC change from baseline by treatment group
- The LSmean (± SE) estimated FVC change from baseline over time by treatment group (as estimated in the primary analysis)

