Subjects who were previously treated with approved IPF therapies (i.e., nintedanib or pirfenidone; unless neither treatment is available in the host country) may be eligible for screening, provided that the subject is not currently receiving treatment with an approved IPF therapy.

NOTE: No subject should discontinue an approved IPF therapy for the purpose of enrolling in this study.

Approximately 340 eligible subjects will be randomized at a 1:1 ratio to Arm A or Arm B, respectively:

Arm A: pamrevlumab, 30 mg/kg IV, Day 1 and every 3 weeks thereafter

Arm B: Matching placebo IV, Day 1 and every 3 weeks thereafter

Randomization will be stratified by GAP stage (I, II, III) derived from the GAP score obtained during screening (See Appendix 5). **NOTE:** For calculation of the GAP score: Use the Best-Test Review (BTR) assessment provided by the spirometry vendor over-reader of the screening value (see Section 6.2.5 and Appendix 5).

The intent of this study is to evaluate the efficacy and safety profile of pamrevlumab as monotherapy in subjects with IPF who were previously treated with an approved therapy but who discontinued that therapy (possible reasons for discontinuation of approved therapy could include, but are not limited to, intolerance or disease progression), unless neither treatment is available in the host country.

During the treatment period, co-administration of an approved IPF therapy (i.e., pirfenidone or nintedanib) is acceptable if clinically indicated in the Investigator's opinion, after assessment of potential risks/benefits of such combination with blinded study treatment. However, since subjects either tried and stopped treatment with an approved IPF therapy, or have no such treatment available, it is not expected that many subjects will resume treatment with an approved IPF therapy during this study.

Subjects who complete the Week 48 visit of the main study (regardless of the number of study drug infusions received) will be eligible to participate in the optional open-label extension (OLE) phase of the study that offers continuing access to pamrevlumab regardless of randomization assignment in the main study. Details of this OLE phase are outlined in Appendix 6.

Subjects who discontinue study treatment for any reason should be encouraged to remain in the study and be followed for all study visits and assessments.

The following assessments will be assessed centrally:

- Pulmonary function tests (PFTs)

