4. SELECTION AND WITHDRAWAL OF SUBJECTS

4.1. Subject Inclusion Criteria

In order to be eligible for inclusion in this trial, a subject must meet all of the following:

1. Age 40 to 85 years, inclusive, at screening initiation.
2. Diagnosis of IPF as defined by ATS/ERS/JRS/ALAT guidelines (Raghu 2018).
3. IPF diagnosis within the past 7 years, with onset defined as the date of the first recorded diagnosis of IPF by HRCT and/or surgical lung biopsy (SLB), or other appropriate tissue sample (e.g., cryobiopsy) in the medical history.
4. Interstitial pulmonary fibrosis defined by HRCT scan at screening, with evidence of $\geq 10\%$ to $< 50\%$ parenchymal fibrosis (reticulation) and $< 25\%$ honeycombing, within the whole lung. **NOTE:** this requires confirmation by an Independent Radiology Imaging Review Group, prior to randomization. If a recent HRCT scan (within 3 months prior to screening) is available, it can be utilized for screening purposes, provided it is submitted and evaluated by the Independent Radiology Imaging Review Group, is adhering to the same imaging acquisition parameters detailed in the Imaging Core Manual (ICM), and is either using the same accredited scanner, or is performed using the same modality, as the on-study HRCT scans.
5. FVCpp value $> 45\%$ and $< 95\%$ at Screening and Day 1 (prior to randomization).
6. Diffusing capacity of the lungs for carbon monoxide (DLCO) percent predicted and corrected by Hb value $\geq 25\%$ and $\leq 90\%$ at screening (determined locally). If a DLCO is available within 3 months prior to screening, it can be utilized for screening purposes.
7. Both FVC and DLCO testing must be representative of the IPF underlying disease (i.e. have been obtained in absence of an acute respiratory event [e.g. lung infection, cold] or other events that are known to affect PFT testing results [e.g., broken rib, chest pain, other]).
8. Previously treated with an approved IPF therapy (i.e., pirfenidone or nintedanib) but discontinued at least 1 week prior to screening, unless neither treatment is available in the host country. **NOTE:** no subject should discontinue approved therapy for the purpose of enrolling in this study.

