APPENDIX 2. ANALYSIS OF ASSOCIATION BETWEEN QLF AND OS

Cox proportional hazard (PH) analyses on the association between QLF and overall survival (OS) will be performed for the ITT population including both double-blind and OLE periods. The hazard ratio and its corresponding 95% CI between QLF Test Group vs QLF Reference Group. A stratified log-rank test stratified by randomization stratification factor will be used for treatment comparison.

No imputation will be performed on missing data. On-treatment analysis will be optional.

- QLF as a predictor:
- 1. To investigate whether baseline QLF is a significant predictor of mortality, a Cox PH model will include electronic data capture (EDC) GAP stage (I/II/III), and prior IPF treatment (Yes/No) as covariates, baseline QLF% (cutoff such as 15%, 20%, or 25%) as the predictor variable.
- 2. Similar analysis on baseline QLF volume (ml) will be performed as in 1), using baseline QLF volume (ml) (cutoff such as 300ml, 400ml, and 500ml) as the predictor variable.
- 3. In addition, Cox PH model including EDC GAP stage (I/II/III), and prior IPF treatment (Yes/No) as covariates, baseline QLF% or QLF volume (ml) (as a continuous variable) as the predictor variable, will be performed.
 - Change from baseline in QLF at Week 24 as a predictor
- 1. In addition, to investigate the association between change from baseline in QLF% (baseline to Week 24) and OS, the Cox PH model will include EDC GAP stage (I/II/III), prior IPF treatment (Yes/No), and baseline QLF% (as a continuous variable) as covariates, and category in change from baseline in QLF% (e.g., ≥2% vs <2%) as the predictor variable.
- 2. Similar analysis on QLF volume (ml) change from baseline will be performed as in 4) with baseline QLF% replaced with baseline QLF volume as a continuous covariate, and change from baseline in QLF volume (ml) as the predictor variable with a cutoff (e.g., ≥40 mL vs <40mL) will be performed.

STATISTICAL ANALYSIS PLAN

TITLE PAGE

A Phase 3, Randomized, Double-Blind, Placebo-

STUDY TITLE: Controlled Efficacy and Safety Study of Pamrevlumab in

Subjects with Idiopathic Pulmonary Fibrosis (IPF)

PROTOCOL NUMBER: FGCL-3019-095 (ZEPHYRUS 2)

FibroGen, Inc.

STUDY SPONSOR: [name]

[name]

STUDY DRUG: Pamrevlumab

INDICATION: Idiopathic Pulmonary Fibrosis (IPF)

PROTOCOL VERSION: Version 2.0

SAP VERSION Final V1.0 (Double-Blind Period)

RELEASE DATE: 12Jun2023

CONFIDENTIALITY STATEMENT

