3.3. Randomization and Treatment Assignment

Subjects will be randomized in a 1:1 ratio to one of the two study treatment arms as follows:

- Arm A: pamrevlumab, 30 mg/kg IV, Q3W (every 3 weeks)
- Arm B: matching placebo IV, Q3W

Randomization is stratified by GAP stage (I, II, III) derived from the GAP score obtained at screening (Refer to Appendix 6). Calculation of the GAP score for randomization is based on the Best-Test Review (BTR) assessment provided by the independent central spirometry vendor reader.

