6.7.2.1.5. Population summary for treatment comparison

The hazard ratio and its corresponding 95% CI will be presented. P-value from stratified Logrank test will also be presented.

All time-to-event analyses will include data collected in the double-blind period. The stratified Cox proportional hazard model including baseline FVCpp stratified by randomization stratification factor will be used to estimate the hazard ratio and its corresponding 95% CI. A stratified log-rank test stratified by randomization stratification factor will be used for treatment comparison.

For time from randomization to the first acute IPF exacerbation, all events pre-defined in the adjudication charter will be adjudicated by an independent Adjudication Committee. The adjudicated results will be summarized by categories of confirmed, suspected, or not acute respiratory exacerbation.

In addition, all acute respiratory exacerbations will be further summarized as:

- a triggered acute respiratory exacerbation
- an idiopathic acute exacerbation (i.e., no trigger identified).

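### Prior antifibrotic therapy defines two kinds of enrolled patient and is collected, but no efficacy treatment-effect model adjusts for it; adding it would be a small, nearly free gain in precision

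*SAP*

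**What the plan says.** **Who is enrolled.** Protocol 4.1, inclusion 8, requires prior pirfenidone or nintedanib, "but discontinued at least 1 week prior to screening, unless neither treatment is available in the host country". The trial can therefore contain previously treated patients and patients who never had access to either drug.

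**How they are randomized.** GAP stage is the only stratification factor. SAP 3.3 states: "Randomization is stratified by GAP stage (I, II, III) derived from the GAP score obtained at screening". The protocol synopsis agrees.

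**What the models contain.**
- Primary MMRM (SAP 6.7.1.1.5): treatment, visit and their interaction, with "randomization stratification factor, and covariates (baseline values, sex, age, race group, and height".
- MMRM for QLF volume and the other continuous endpoints (SAP 6.7.2.2.5): the same list, cut down for FVCpp.
- RCM, jump-to-control, tipping-point and ranked ANCOVA (SAP 6.7.1.2.1 to 6.7.1.2.4): baseline FVC, age, sex, race group, height and the stratification factor.
- Time-to-event endpoints (SAP 6.7.2.1.5): "The stratified Cox proportional hazard model including baseline FVCpp stratified by randomization stratification factor", with a log-rank test stratified by the same factor for the treatment comparison.

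Prior antifibrotic use is in none of them.

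**Where the variable does appear.** SAP 6.3.1 lists "prior treatment with an approved IPF therapy (Yes/No" among the baseline characteristics, with nominal between-arm p-values. SAP 6.7.1.4 makes it a subgroup for the primary endpoint, alongside on-study antifibrotic use and region, and SAP 6.7.2.3 repeats the subgroups for the secondary endpoints. In Appendix 2 of the OLE SAP, on QLF and survival, "a Cox PH model will include electronic data capture (EDC) GAP stage (I/II/III), and prior IPF treatment (Yes/No) as covariates".

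**The concern.** Prior antifibrotic use separates two groups that the eligibility rule itself defines. Some patients stopped an approved drug, and the protocol gives intolerance and progression as possible reasons; others had no access to one. The two groups could plausibly decline at different rates. The variable is known at baseline, is in the database, and would cost one degree of freedom.

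If it is prognostic, leaving it out has two consequences. Residual variance is slightly larger than it need be. And if prior use happens to differ between arms, the pre-specified analysis makes no allowance for it. SAP 6.3.1 would display such a difference but gives no rule for acting on it, and subgroup estimates do not adjust the overall estimate. A covariate added after unblinding would be open to challenge as post hoc.

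**Working it through.** **Step 1: reproduce the sample size.** Inputs from Protocol 8.1 and SAP 3.2: difference 120 mL, SD 300 mL, two-sided alpha 0.05, power at least 90%, dropout about 20%.

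- n per arm = 2 × (1.960 + 1.282)² × 300² / 120² = 131.4, so 132 per arm and 264 in total.
- Allowing for dropout: 264 / 0.8 = 330, consistent with the planned 340.
- Completers: 340 × 0.8 = 272. Unadjusted SE = 300 × √(4/272) = 36.4 mL.
- Power = Φ(120/36.4 − 1.96) = 91.0%.

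The stated figure reproduces.

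**Step 2: assumptions.** The documents give neither p, the share of patients with no prior antifibrotic, nor D, the difference in 48-week FVC change between the groups. Both are assumed here: p from 10% to 50%, D from 50 to 150 mL.

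**Step 3: formulas, with N = 272.**
- SD of the chance between-arm difference in share = √(p(1−p) × 4/N)
- 95% range of the shift in the FVC difference = ±1.96 × that SD × D
- Share of variance explained = p(1−p)D² / 300²
- Adjusted SE = 36.4 × √(1 − share of variance explained)

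| p | D | SD of imbalance | 95% range of shift | Variance explained | Adjusted SE | Power |
|---|---|---|---|---|---|---|
| 10% | 50 mL | 3.6 points | ±3.6 mL | 0.25% | 36.3 mL | 91.0% |
| 30% | 100 mL | 5.6 points | ±10.9 mL | 2.3% | 36.0 mL | 91.6% |
| 50% | 150 mL | 6.1 points | ±17.8 mL | 6.25% | 35.2 mL | 92.6% |

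**Step 4: the shift is not an extra error.** In the middle row the unadjusted 95% half-width is 1.96 × 36.4 = 71.3 mL. Removing the imbalance component gives √(71.3² − 10.9²) = 70.5 mL, which is 1.96 times the adjusted SE. The ±10.9 mL is one component of the ±71.3 mL that the unadjusted analysis already reports.

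**Step 5: validity without the covariate.** A simulation of 40,000 trials with no treatment effect (p = 30%, D = 100 mL, N = 272, covariate omitted) gave a mean bias of −0.05 mL and a type I error of 0.0502.

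These figures use the t-test SD of 300 mL. The MMRM already adjusts for baseline FVC, GAP stage, age, sex, race group and height, so the real gain is smaller wherever prior use overlaps with those.

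**The case against.** The strongest reply is that this is a preference about covariates. Randomization balances prior use in expectation, chance imbalance is part of the standard error, and the same complaint could be made about any baseline variable left out. The inputs behind the gain are assumed, and the top of the range for D exceeds the 120 mL drug effect the trial is powered for. The SAP also makes the variable visible, through the baseline comparison and through subgroups by prior use, on-study use and region. All of this stands, and it sets the size of the point.

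A reader might also infer more than the documents support:
- **That the efficacy estimates carry a background-treatment imbalance.** Prior therapy was stopped before screening, so it is not background treatment. Antifibrotic use during the study is post-randomization and falls under the treatment-policy strategy; it could be neither a stratification factor nor a baseline covariate.
- **That the missing-at-random assumption is weakened.** Nothing in the documents shows that dropout depends on prior use, and SAP 6.7.1.2.2 and 6.7.1.2.3 already examine departures from that assumption.
- **That the two SAPs contradict each other.** The OLE SAP models relate QLF, a non-randomized exposure, to survival. They show that the variable is available and thought relevant to survival, not that the treatment comparison needs it.
- **That a Cox covariate would change the time-to-event tests.** The comparison rests on the GAP-stratified log-rank test, which the covariate leaves unchanged.

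What remains is that visibility is not adjustment. Neither the baseline p-values nor the subgroups alter the overall estimate.

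**Conclusion.** The point holds as a small, optional improvement. The eligibility rule creates two groups, and no efficacy treatment-effect model uses the collected variable that separates them. The plan is not biased by this, and its type I error is not inflated.

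Under the assumed ranges with 272 completers, what is forgone is a reduction in SE from 36.4 mL to between 36.3 and 35.2 mL, or at most 1.6 points of power (91.0% to 92.6%). The chance shift left unadjusted is about ±4 to ±18 mL against a target of 120 mL. These are upper estimates, because covariates already in the model may carry part of the same information. If few untreated patients are enrolled, the gain is close to nil.

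For the Cox model, omitting a prognostic factor can pull the hazard ratio somewhat toward 1; it does not create a spurious effect.

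**What to change.** Before unblinding, by SAP amendment (SAP Section 1 provides for changes after signoff):

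1. Add prior approved IPF therapy (Yes/No) as a baseline fixed effect in the primary MMRM of SAP 6.7.1.1.5.
2. Add the same term to the RCM and to the jump-to-control, tipping-point and ranked ANCOVA models. For jump-to-control and tipping-point, include it in the imputation step as well: the sample code in SAP Appendices 7.2 and 7.3 imputes from treatment, baseline and visit values only.
3. Add it as a covariate in the Cox model of SAP 6.7.2.1.5, and state that this changes the hazard ratio and its confidence interval but not the log-rank p-value.
4. Keep the planned baseline table and subgroup analyses.

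The cost is one degree of freedom per model, edits to the sample code and a short amendment. No new data are needed and the randomization is untouched. The drawback is some overlap with race group. There is precedent for extending the list: race group is in the SAP's primary model but not among the covariates in Protocol 8.3.4.1.
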